5.3.4.5 Deaths

All deaths that occur during the protocol-specified adverse event reporting period (see Section 5.3.1), regardless of relationship to study drug, must be recorded on the Adverse Event eCRF and immediately reported to the Sponsor (see Section 5.4).

Death should be considered an outcome and not a distinct event. The event or condition that caused or contributed to the fatal outcome should be recorded as the single medical concept on the Adverse Event eCRF. Generally, only one such event should be reported.

If the death is attributed to progression of MDS, "MDS progression" should be recorded on the Adverse Event eCRF.

5.3.4.6 Preexisting Medical Conditions

A preexisting medical condition is one that is present at the screening visit for this study. Such conditions should be recorded on the General Medical History and Baseline Conditions eCRF.

A preexisting medical condition should be recorded as an adverse event only if the frequency, severity, or character of the condition worsens during the study. When recording such events on the Adverse Event eCRF, it is important to convey the concept that the preexisting condition has changed by including applicable descriptors.

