4.4.1.2 Physical Examinations

A complete physical examination should include an evaluation of the head, eyes, ears, nose, and throat, and the cardiovascular, dermatological, musculoskeletal, respiratory, gastrointestinal, genitourinary, and neurological systems. Any abnormalities identified at screening should be recorded on the General Medical History and Baseline Conditions eCRF.

At subsequent visits (or as clinically indicated), limited, symptom-directed physical examinations should be performed. Changes from baseline abnormalities should be recorded in patient notes. New or worsened clinically significant abnormalities should be recorded as adverse events on the Adverse Event eCRF.

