4.4.2 Timing of Study Assessments

4.4.2.1 Screening Assessments

Written informed consent for participation in the study must be obtained before performing any study-specific screening tests or evaluations. Informed Consent Forms for enrolled patients and for patients who are not subsequently enrolled will be maintained at the study site.

Screening tests and evaluations will be performed within 14 days prior to the start of study drug administration, unless otherwise specified.

Results of standard-of-care tests or examinations performed prior to obtaining informed consent and within 14 days prior to the start of study drug administration may be used; such tests do not need to be repeated for screening. These will include the following:

Recormon—F. Hoffmann-La Roche Ltd

Protocol ML29005, Version 3.0 dated 12 Sep 2016

29

- Review and documentation of demographics data and medical history
- Review and documentation of MDS diagnosis
- IPSS score
- Physical examination
- Vital sign measurements
- Haematology and biochemistry laboratory tests
- AE recording (Note: after informed consent has been obtained but prior to initiation of study drug, only SAEs caused by a protocol-mandated intervention should be reported).
- Recording concomitant treatments and therapies
- Recording RBC transfusion needed within the past 8 weeks
- Serum pregnancy test for female patients of childbearing potential. Patients who are amenorrheic for at least 12 months are not considered of childbearing potential.

All screening evaluations must be completed and reviewed to confirm that patients meet all eligibility criteria before enrolment. The investigator will maintain a screening log to record details of all patients screened and to confirm eligibility or record reasons for screening failure, as applicable.

Patients who fail screening may be re-screened if it is considered likely that they could later become eligible. There is a limit of 2 screening attempts for each patient. Re-consenting process must be performed.

Please see Appendix 1 for the schedule of screening assessments.

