4.4.2.2 Assessments during Treatment

All assessments must be performed on the day of the specified visit (V1 – V4), unless a time window is specified in the schedule of assessments (see Appendix 1). Assessments scheduled on the visit date should be performed prior to administration of study treatment, unless otherwise noted in the schedule of assessments.

At each treatment visit, patients will undergo the following assessments:

- Physical examination and measurements of vital signs
- Routine laboratory tests (see section 4.4.1.4 for details about individual laboratory assays). The results from these tests should be available on visit date prior to the Recormon® administration.
- AE recording
- Recording concomitant treatments and therapies
- Recording RBC transfusion needed from previous visit
- Recormon® dose adjustment will be performed at week 4±1 (see section 4.2.2.1 for details about dose adjustment)

Please see Appendix 1 for the schedule of assessments performed during the treatment period.

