5.3.1 Adverse Event Reporting Period

Investigators will seek information on adverse events at each patient contact. All adverse events, whether reported by the patient or noted by study personnel, will be recorded in the patient’s medical record and on the Adverse Event eCRF.

After informed consent has been obtained **but prior to initiation of study drug**, only serious adverse events caused by a protocol-mandated intervention should be reported

After initiation of study drug, all adverse events, regardless of relationship to study drug, will be reported until 4 weeks (28 days) after the last dose of study drug (End of study/early withdrawal visit)

Resolution of adverse events and serious adverse events including dates should be followed-up until it is known or end of study/early withdrawal visit, whichever occurs first and documented on the Adverse Events eCRF and in the patient’s medical record to facilitate source data verification.

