6.5 SAFETY ANALYSES

All patients who have received at least one dose of study medication, whether prematurely withdrawal or not will be included in the safety analysis.

The safety parameters will be vital signs, AEs, SAEs and the safety laboratory assessments including serum ferritin. All clinical AEs and SAEs as well as laboratory abnormalities will be recorded and graded according to the NCI-CTCAE version 4.0.

Adverse events will be coded using the Medical Dictionary for Regulatory Activities (MedDRA). The incidence of all AEs/SAEs will be summarized according to the primary system-organ class and by preferred terms.

Safety laboratory parameters (Section 4.4.1.4) will be summarized and at least presented descriptively, and the selected laboratory parameters may also be displayed graphically.

Further details about planned safety analyses will be presented in Statistical Analysis Plan (SAP)

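### Pre-existing conditions are cut off at screening, not first dose: a condition starting in between is an AE under 4.4.1.2, not reportable under 5.3.1, and not baseline under 5.3.4.6

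*Protocol*

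**What the plan says.** All references are to the protocol.

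- **Baseline cut-off (5.3.4.6).** "A preexisting medical condition is one that is present at the screening visit for this study". Such conditions go on the General Medical History and Baseline Conditions eCRF. Section 4.4.1.2 likewise sends abnormalities found at screening to that form.
- **Length of the gap (4.4.2.1).** "Screening tests and evaluations will be performed within 14 days prior to the start of study drug administration, unless otherwise specified".
- **Visits after screening (4.4.1.2).** "At subsequent visits (or as clinically indicated), limited, symptom-directed physical examinations should be performed", and then "New or worsened clinically significant abnormalities should be recorded as adverse events on the Adverse Event eCRF". Neither sentence is limited to visits after drug has started.
- **V1 is pre-dose (4.4.2.2).** "Assessments scheduled on the visit date should be performed prior to administration of study treatment, unless otherwise noted in the schedule of assessments". This covers V1 to V4, and AE recording is among the listed assessments. Appendix 1 marks physical examination, vital signs, laboratory tests and adverse events at V1, and no footnote moves any of them to after the dose.
- **Reporting period (5.3.1).** Between consent and the start of drug, "only serious adverse events caused by a protocol-mandated intervention should be reported". Reporting of all AEs begins once drug has started. Section 4.4.2.1 repeats the pre-dose limit in its list of screening assessments.
- **Analysis (6.5).** "The incidence of all AEs/SAEs will be summarized according to the primary system-organ class and by preferred terms". The section leaves further detail of the safety analyses to the SAP.

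**The concern.** Three sections govern a condition that appears between the screening visit and the first dose, and they give three different answers. The site has to choose. If it follows 4.4.1.2, a condition that began before any Recormon goes on the Adverse Event eCRF. If it follows 5.3.1, the condition has no assigned page: it is not a reportable AE, and 5.3.4.6 keeps it off the baseline form. If it persists and is noticed again at week 4, nothing on the baseline form shows that it came before the drug, and it can then be entered as a new on-drug event.

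The safety outcome in 3.4.2 is the incidence, nature and severity of adverse events. With one arm and no control, no comparator would reveal that pre-drug conditions had been counted. Section 4.4.2.1 also lists AE recording at screening (limited to protocol-caused SAEs), while Appendix 1 has no AE mark at screening and an unqualified one at V1.

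**Working it through.** **Step 1. Follow one condition through the rules.** Take a non-serious, clinically significant condition, not caused by a study procedure, that starts after the screening visit and is found at the V1 examination before the first injection.

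| Section | Treatment of the condition |
|---|---|
| 5.3.4.6 | Absent at screening, so not pre-existing |
| 4.4.1.2 with 4.4.2.2 and Appendix 1 | New finding at a visit after screening, so recorded as an AE |
| 5.3.1 (and 4.4.2.1) | Before drug, and not a protocol-caused SAE, so not reported |

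No other section assigns it a place on an eCRF.

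**Step 2. Check whether the plan's own safety figure is affected.** Section 6.1 gives at least a 95% chance of seeing one or more cases of an event with true proportion 0.0274 in 108 evaluable patients.

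- 1 − (1 − 0.0274)^108 = 0.9502, which agrees.
- Smallest proportion detectable at 95%: 1 − 0.05^(1/108) = 0.02736, which agrees with 0.0274.
- Enrolment: 108 / (1 − 0.10) = 120, which agrees.

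The recording conflict alters none of these, nor the primary endpoint.

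**Step 3. Illustrate the possible scale.** The protocol gives no background event rate, so this is an assumption and not an estimate. Assume a constant background rate, a gap of 7 to 14 days, every gap event recorded as an AE, no onset rule in the analysis, and 105 to 112 days from first dose to four weeks after the last dose (last dose at week 11 or week 12).

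Share of recorded background events that precede the drug = gap / (gap + on-study days):

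- 7 / (7 + 112) = 5.9%; 7 / (7 + 105) = 6.3%
- 14 / (14 + 112) = 11.1%; 14 / (14 + 105) = 11.8%

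Counted incidence for the full 14-day gap, if the event is entirely background = 1 − (1 − true incidence)^((gap + on-study days) / on-study days):

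- True 10%: 1 − 0.90^(126/112) = 11.2%; 1 − 0.90^(119/105) = 11.3%
- True 2.74%: 1 − 0.9726^(126/112) = 3.08%; 1 − 0.9726^(119/105) = 3.10%

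These figures lean high. Many patients will have a shorter gap, some sites will follow 5.3.1, and 4.4.1.2 captures only clinically significant findings at a limited, symptom-directed examination.

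**The case against.** The strongest reply is that the protocol already has a controlling rule. Section 5.2.1 defines an AE in a subject who has been given a product, and the only pre-treatment case it names is an event related to a protocol-mandated intervention. Section 5.3.1 is the dedicated reporting-period rule and draws the same line. Read together, these favour leaving gap-onset conditions out, and a general sentence about physical examinations should not override them. This largely stands as a guide to intent. It does not settle the matter for a site, because 4.4.1.2 and Appendix 1 carry no such limit, and excluding the condition as an AE still leaves it without a place on the baseline form.

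Four stronger readings are tempting, and the document does not support them.

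- **That 5.3.4.6 by itself turns anything absent at screening into an AE.** It says only when a condition already present becomes one. The conflict arises from 4.4.1.2 against 5.3.1.
- **That nothing is reported before the first dose.** Protocol-caused SAEs are reported from consent.
- **That Appendix 1 has its AE marks the wrong way round.** Section 4.4.2.1 already instructs AE recording at screening, so the missing mark is an omission in the table. V1 is the day of the first dose, so an AE mark there has a legitimate use. The mismatch is real but smaller.
- **That the reported AE incidence will be inflated because 6.5 has no onset limit.** A treatment-emergent rule is commonly set in an SAP, and 6.5 defers to one that is not shown. Such a rule could remove recorded pre-dose events by onset date, so the absence of the limit from 6.5 is no finding.

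An onset rule would not repair everything. It cannot help where a site left the condition off the eCRFs at V1 and later entered it as new. Under 5.3.4.3 a persistent event is recorded once with its severity updated, so a pre-dose record that worsens on drug could keep its pre-dose start and be dropped by a filter on onset alone.

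**Conclusion.** The point holds as a conflict in data-collection rules. The baseline cut-off lies up to 14 days before the first dose, and new findings in that gap are handled differently by 4.4.1.2, 5.3.1 and 5.3.4.6. Pre-drug conditions may therefore be recorded as AEs, and whether they are depends on which section a site follows.

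The size is modest and cannot be determined from the protocol. The illustration above (about 6% to 12% of recorded background events preceding the drug) depends on a constant rate, complete recording of gap events and no onset rule, none of which the protocol states. Bias in the reported incidence is possible but not demonstrated. The primary endpoint, sample size and stated precision are unaffected. The correction is still worthwhile because it concerns the safety outcome of an uncontrolled study, and the V1 data it needs are already collected before dosing.

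**What to change.** 1. In 5.3.4.6, define a pre-existing condition as one present before the first dose of study drug, whether found at screening or at the pre-dose V1 assessment.
2. In 4.4.1.2 and 4.4.2.2, direct new findings at the pre-dose V1 assessment to the General Medical History and Baseline Conditions eCRF, keeping the 5.3.1 exception for SAEs caused by a protocol-mandated intervention. Later worsening on drug then becomes an AE under the existing rule in 5.3.4.6.
3. In Appendix 1, mark screening for protocol-caused SAEs, and state that the V1 AE entry covers events from the first dose onward plus any protocol-caused SAEs before it.

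No change to 6.5 is needed for this point. The cost is a minor protocol amendment, with the approvals that 9.5 requires, and an update to the eCRF completion guide. No assessment is added.

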5.3.4.7 Hospitalization or Prolonged Hospitalization

Any adverse event that results in hospitalization or prolonged hospitalization should be documented and reported as a serious adverse event (per the definition of serious adverse event in Section 5.2.2), except as outlined below.

The following hospitalization scenarios are not considered to be serious adverse events:

- Hospitalization for respite care
- Planned hospitalization required by the protocol
- Hospitalization for a preexisting condition, provided that all of the following criteria are met:
 - The hospitalization was planned prior to the study or was scheduled during the study when elective surgery became necessary because of the expected normal progression of the disease
 - The patient has not suffered an adverse event

5.3.4.8 Overdoses

Study drug overdose is the accidental or intentional use of the drug in an amount higher than the dose being studied. An overdose or incorrect administration of study drug is not an adverse event unless it results in untoward medical effects.

Any study drug overdose or incorrect administration of study drug should be noted on the Study Drug Administration eCRF.

All adverse events associated with an overdose or incorrect administration of study drug should be recorded on the Adverse Event eCRF. If the associated adverse event fulfills serious criteria, the event should be reported to the Sponsor immediately (i.e., no more than 24 hours after learning of the event; see Section 5.4).

5.4 IMMEDIATE REPORTING REQUIREMENTS FROM INVESTIGATOR TO SPONSOR

To ensure the safety of study patients, emergency Medical Call contact will be available 24 hours per day, 7 days per week. Medical Monitor contact information will be distributed to all investigators.

Emergency Medical Contact:

Medical Monitor (Roche Medical Responsible) contact Information

Medical Monitor: Dr. [REDACTED], MD.

Telephone: [REDACTED]

Certain events require immediate reporting to allow the Sponsor to take appropriate measures to address potential new risks in a clinical trial. The investigator must report such events to the Sponsor immediately; under no circumstances should reporting take place more than 24 hours after the investigator learns of the event. The following is a list of events that the investigator must report to the Sponsor within 24 hours after learning of the event, regardless of relationship to study drug:

- Serious adverse events
- Pregnancies

The investigator must report new significant follow-up information for these events to the Sponsor immediately (i.e., no more than 24 hours after becoming aware of the information). New significant information includes the following:

- New signs or symptoms or a change in the diagnosis
- Significant new diagnostic test results
- Change in causality based on new information
- Change in the event's outcome, including recovery
- Additional narrative information on the clinical course of the event

Investigators must also comply with local requirements for reporting serious adverse events to the local health authority and IRB/EC.

5.4.1 Reporting Requirements for Serious Adverse Events

For reports of serious adverse events, investigators should record all case details that can be gathered immediately (i.e., within 24 hours) on the Adverse Event page and

Forward the paper SAE reporting form via fax or email to:

Local safety responsible

Fax: [REDACTED]

Email: [contact]

5.4.2 Reporting Requirements for Pregnancies

No data are available from adequate, controlled studies of Recormon® in pregnant women. Therefore, women of childbearing potential must have a serum pregnancy test at screening and must use a reliable method of contraception throughout the study.

A female subject must be instructed to stop taking the study medication and immediately inform the investigator if she becomes pregnant during the study. The investigator should report all pregnancies within 24 hours after becoming aware of the pregnancy to the sponsor using the Pregnancy Reporting Form.

Forward the paper pregnancy reporting form via fax or email to:

Local safety responsible

Fax: [REDACTED]

Email: [contact]

The investigator should counsel the subject; discuss the risks of continuing with the pregnancy and the possible effects on the fetus. Monitoring of the patient should continue until conclusion of the pregnancy. Pregnancies occurring up to 90 days after the completion of the study medication must also be reported to the investigator.

6. STATISTICAL CONSIDERATIONS AND ANALYSIS PLAN

Descriptive statistics will be used for baseline characteristics. The interim data analysis will be performed when the first 30 patients are completing the 12-week treatment period.

6.1 DETERMINATION OF SAMPLE SIZE

Sample size based on a 5% significance level and the 80% power with 10% drop out resulting of 120 patients in total.

- Safety: Assuming a 10% withdrawal rate, 120 patients will be enrolled such that we expect 108 patients will not withdraw and will remain evaluable. With 108 evaluable patients in this study, the sample size is sufficient to have at least 95% probability of observing a particular adverse event in at least one patient in this study, if the true proportion of patients in the target population as a whole who experience this event is 0.0274 i.e. approximately 1 in every 37 patients.
- Efficacy: Assuming a 10% withdrawal rate, 120 patients will be enrolled such that we expect 108 patients will not withdraw and will remain evaluable. To give an estimate of the precision of this study in terms of estimating the proportion of patients with erythroid response, then with 108 evaluable patients in this study, if the observed proportion of patients with erythroid response in the study were 0.25, then the half width of the 95% confidence interval for this proportion would be 0.0817 (i.e. the 95% confidence interval would be 0.1683 to 0.3317).

6.2 ANALYSIS POPULATION

The efficacy analysis will be performed based on the intent-to-treat (ITT) population defined as all enrolled patients who receive at least one dose of study medication.

The Safety population will include all patients who receive at least one dose of study medication.

6.3 INTERIM ANALYSIS

An interim analysis of primary end point (erythroid response at week 12 according to IWG 2006 definition) will be undertaken when the first 30 patients have completed their 12-week treatment, and safety data will also be summarized at that time.

Further details regarding the planned interim analysis will be presented in the Statistical Analysis Plan (SAP).

6.4 EFFICACY ANALYSES

The efficacy analyses will include all enrolled patients who receive at least one dose of study medication. Efficacy endpoint will be summarized based on ITT population.

Subgroup analysis may be performed for efficacy analysis.

6.4.1 Primary Efficacy Endpoint

The Intent-To-Treat (ITT) analysis of the primary outcome variables is planned. Patients who meet the evaluable criteria as specified in the analysis plan will be included in the per protocol

For the primary endpoint of erythroid response, the percentages of patients who achieve the target haemoglobin increase by ≥ 1.5 g/dL, or reduction of units of RBC transfusions by an absolute number at week 12 will be summarized in the table.

6.4.2 Secondary Efficacy Endpoints

Secondary efficacy endpoints include platelet and neutrophil response at week 12, defined by the following IWG 2006 criteria and will analyzed for the PP population.

- % patients with platelet response (pre-treatment $< 100 \times 10^9/L$) at week 12 defined by IWG 2006 as following:
 - Absolute increase of $\geq 30 \times 10^9/L$ for patients starting with $> 20 \times 10^9/L$ platelets (Increase from $< 20 \times 10^9/L$ to $> 20 \times 10^9/L$ and by at least 100%)
- % patients with neutrophil response (pre-treatment $< 1.0 \times 10^9/L$) at week 12 defined by IWG 2006 as following:
 - At least 100% increase and an absolute increase $> 0.5 \times 10^9/L$

The percentages of patient who achieve the above hematologic responses at week 12, according to the IWG 2006 criteria will be presented in summary tables.

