Efficacy: Assuming a 10% withdrawal rate, 120 patients will be enrolled such that we expect 108 patients will not withdraw and will remain evaluable. To give an estimate of the precision of this study in terms of estimating the proportion of patients with erythroid response, then with 108 evaluable patients in this study, if the observed proportion of patients with erythroid response in the study were 0.25, then the half width of the 95% confidence interval for this proportion would be 0.0817 (i.e. the 95% confidence interval would be 0.1683 to 0.3317).

Analysis Population

The efficacy analysis will be performed based on the intent-to-treat (ITT) population defined as all enrolled patients who receive at least one dose of study medication.

The Safety population will include all patients who receive at least one dose of study medication.

Interim Analysis

An interim analysis of primary end point (erythroid response at week 12 according to IWG 2006 definition) will be undertaken when the first 30 patients have completed their 12-week treatment, and safety data will also be summarized at that time.

Further details regarding the planned interim analysis will be presented in the Statistical Analysis Plan (SAP).

Efficacy Analysis

The efficacy analyses will include all enrolled patients who receive at least one dose of study medication. Efficacy endpoint will be summarized based on ITT population. Subgroup analysis may be performed for efficacy analysis.

Primary Efficacy Endpoint

Intent-To-Treat (ITT) analysis of the primary outcome variables is planned. Patients who meet the evaluable criteria as specified in the analysis plan will be included in the per protocol

For the primary endpoint of erythroid response, the percentages of patients who achieve the target haemoglobin increase by ≥ 1.5 g/dL, or reduction of units of RBC transfusions by an absolute number at week 12 will be summarized in table.

Secondary Efficacy Endpoints

Secondary efficacy endpoints include platelet and neutrophil response at week 12, defined by the following IWG 2006 criteria and will analyzed for the PP population.

- % patients with platelet response (pre-treatment $< 100 \times 10^9/L$) at week 12 defined by IWG 2006 as following;
- Absolute increase of $\geq 30 \times 10^9/L$ for patients starting with $> 20 \times 10^9/L$ platelets (Increase from $< 20 \times 10^9/L$ to $> 20 \times 10^9/L$ and by at least 100%)

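### The protocol assigns platelet and neutrophil response to the PP population in Section 6.4.2 and the synopsis, but its general rule puts all efficacy analyses on ITT without exception

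*Protocol*

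**What the plan says.** The general rule appears in three places.

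- Section 6.2: "The efficacy analysis will be performed based on the intent-to-treat (ITT) population", with ITT defined as enrolled patients who received at least one dose. The only other set listed there is for safety: "The Safety population will include all patients who receive at least one dose of study medication".
- Section 6.4, the parent of 6.4.1 and 6.4.2: "The efficacy analyses will include all enrolled patients who receive at least one dose of study medication", followed by "Efficacy endpoint will be summarized based on ITT population".
- The synopsis repeats both, under Analysis Population ("The efficacy analysis will be performed based on the intent-to-treat (ITT) population defined as all enrolled patients") and under Efficacy Analysis.

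The specific statement is in Section 6.4.2: "Secondary efficacy endpoints include platelet and neutrophil response at week 12, defined by the following IWG 2006 criteria and will analyzed for the PP population". The synopsis paragraph on secondary efficacy endpoints has the same words: "defined by the following IWG 2006 criteria and will analyzed for the PP population".

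The only other current mention of a per-protocol set is in Section 6.4.1 and its synopsis copy: "Patients who meet the evaluable criteria as specified in the analysis plan will be included in the per protocol". The sentence stops there and does not say which analysis that set serves.

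**The concern.** Two analysts who both follow the protocol could report platelet and neutrophil response on different sets. One would use all dosed patients with the qualifying baseline count. The other would use only those who also meet per-protocol criteria.

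The choice can matter because a PP set may select patients on what happens after treatment starts. Section 4.5.1.1 lists lack of response among the reasons for stopping study drug, and Section 3.1.1 has patients stop when haemoglobin reaches the upper threshold. If the PP criteria required completion of 12 weeks (an assumption, since the protocol leaves the criteria to the analysis plan), exclusion could follow either a poor or a good haemoglobin response. The direction of any shift therefore cannot be predicted.

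The study is open-label. Unless the set is settled before analysis, the denominator could be chosen after the results are seen.

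**Working it through.** **Text comparison**

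| Place in the protocol | Set for platelet and neutrophil response |
|---|---|
| 6.2 Analysis Population | ITT, no exception; PP not listed |
| 6.4 Efficacy Analyses | All enrolled and dosed patients, no exception |
| Synopsis, Analysis Population and Efficacy Analysis | ITT, no exception |
| 6.4.2 Secondary Efficacy Endpoints | PP |
| Synopsis, Secondary Efficacy Endpoints | PP |

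1. Section 3.4.1 lists platelet and neutrophil response as secondary efficacy outcomes, so statements about the efficacy analyses include them.
2. An analysis restricted to PP does not include every enrolled, dosed patient unless the two sets happen to coincide. Sections 6.4 and 6.4.2 therefore cannot both be followed in general.
3. All five statements are current text. The rationale for Version 3.0 names 6.2, 6.4 and 6.4.1 as the sections updated for the efficacy analysis population, and does not name 6.4.2. That fits an oversight or a deliberate choice equally well, so it does not settle the intent. The contradiction stands without it.

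**The plan's own figures (Section 6.1)**

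- Enrolment: 108 / (1 − 0.10) = 120, as stated.
- Half width of the 95% confidence interval at 0.25: 1.96 × √(0.25 × 0.75 / 108) = 0.0817, giving 0.1683 to 0.3317, as stated.

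Both reproduce. They are planning figures for safety and erythroid response; the protocol gives no PP size.

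**How far apart the two sets could be (illustration)**

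Assumptions: PP excludes only withdrawn patients; the same share is excluded among patients with the qualifying cytopenia; response status is known for everyone.

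- Expected withdrawals: 120 × 0.10 = 12, so the excluded fraction is f = 12/120 = 0.10.
- For an ITT rate p between f and 1 − f, the PP rate lies between (p − f)/(1 − f), when every excluded patient responded, and p/(1 − f), when none did.
- Width of that range: f/(1 − f) = 12/108 = 0.111, or 11.1 points, for any p from 0.10 to 0.90.
- Largest gap upward: pf/(1 − f). Largest gap downward: (1 − p)f/(1 − f).

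| ITT rate p | Lowest PP rate | Highest PP rate | Gap down | Gap up |
|---|---|---|---|---|
| 0.10 | 0/0.9 = 0.000 | 0.10/0.9 = 0.111 | 0.100 | 0.011 |
| 0.25 | 0.15/0.9 = 0.167 | 0.25/0.9 = 0.278 | 0.083 | 0.028 |
| 0.90 | 0.80/0.9 = 0.889 | 0.90/0.9 = 1.000 | 0.011 | 0.100 |

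The 11.1 points is the width of the range of possible PP rates. The largest one-way difference between PP and ITT is 10.0 points.

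**If excluded patients count as non-responders instead**

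This replaces the assumption that their response is known. A PP rate of 27/108 = 25% then becomes 27/120 = 22.5% on ITT. With 5% to 30% excluded, a 25% PP rate corresponds to 0.25 × 0.95 = 23.8% down to 0.25 × 0.70 = 17.5%.

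**The case against.** The strongest defence is that the specific rule governs. Section 6.4 speaks of the efficacy endpoint in the singular, 6.4.1 gives ITT to the primary outcome, 6.4.2 gives PP to the secondary ones, and the synopsis repeats the split. On that reading the only fault is an unstated exception. This is a possible reading, but it does not remove the conflict: the opening sentence of 6.4 is plural and unrestricted, and 6.2 allows no exception.

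A second defence is that the SAP may settle the matter. The evaluability criteria may properly be left to the SAP, and their absence from the protocol is not a defect. But when the protocol has fixed two sets for the same endpoints, whichever one the SAP adopts departs from one of the protocol's statements.

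A third objection is to the numbers, and much of it stands. The 11.1 points should not be read as the largest PP–ITT difference. Nor does either figure limit the real discrepancy: a PP set that also excluded protocol violators could differ by more, and withdrawn patients may have no week-12 value. The finding does not depend on these figures.

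It can also be said that correcting the contradiction requires only one clear statement of which set applies, and that an ITT companion to a PP analysis is a preference. The contradiction itself does require no more. The companion is recommended because a PP set can select on post-baseline events.

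**Conclusion.** The point holds. The current protocol gives two analysis sets for platelet and neutrophil response, in the body and within the synopsis, and the intended one cannot be recovered from the text.

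The consequence is modest. Both endpoints are percentages for summary tables, no test is planned for them, and the sample-size section does not use them. The primary endpoint is explicitly ITT and is unaffected. The effect on the reported rates cannot be determined in size or direction; the 10.0-point one-way maximum holds only under the three stated assumptions and is not an estimate. The text should be corrected before analysis.

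**What to change.** 1. In Section 6.4.2 and the matching synopsis paragraph, replace PP with ITT, among patients with the stated pre-treatment cytopenia. This follows the protocol's own general rule and avoids selection on post-baseline events.
2. If PP was intended for the secondary endpoints, state that exception in 6.2, 6.4 and the synopsis, list PP in 6.2, and report the ITT percentages beside the PP ones.
3. In 6.4.1 and the synopsis, either delete the unfinished sentence or complete it as a supportive PP analysis, with PP listed in 6.2 and its criteria left to the SAP.

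The cost is a few wording changes and minor table work; no new data are needed. The reported secondary rates may differ, in either direction, from those on a PP set.
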